Incomplete emptying due to underactive bladder is a poorly understood health concern that symptomatically affects up to 40% of the population, with the highest prevalence of symptoms in older men and women (Jeong et al. 2012, Osman et al. 2014). Despite the high prevalence of symptoms, the diagnosis of an underactive bladder remains low due to the lack of consistent terminology and standardized diagnostic criteria. This results in defining underactive bladder by a symptom complex that may involve reduced motor drive (detrusor underactivity) during bladder emptying and/or reduced sensory drive during filling and emptying (Chapple et al. 2015). Symptoms experienced by persons with underactive bladder include nocturia, urinary frequency, urgency, incontinence, slow stream, hesitancy, straining, and sensation of incomplete emptying (Gammie et al. 2016, Uren et al. 2017). The most common symptoms are nocturia, slow stream, frequency, hesitancy, and the impact of these symptoms on quality of life is substantial for many patients (Gammie et al. 2016, Uren et al. 2017).

The management options for persons with underactive bladder include double-void, intermittent self-catheterization, or pharmacotherapy (Miyazato et al. 2013). However, these treatments are associated with poor quality of life and patients often fail to completely resolve the lower urinary tract symptoms (LUTS). There is a need to clarify the pathological mechanisms underlying underactive bladder to improve therapeutic outcomes. One approach to clarify reduced sensory drive is to evaluate the functional integrity of sensory nerves with quantitative sensory testing (Ukimura et al. 2004, Kenton et al. 2007). Current perception threshold (CPT) testing delivers electrical stimulation to activate nerve fibers that evoke sensory perception, and changes in bladder sensory pathways were demonstrated in persons with diabetic detrusor underactivity (Lee et al. 2009). These diagnostic tests, however, have not been applied to neurologically intact adult women with underactive bladder and may provide insight into pathological sensory dysfunction.

The proposed research will quantify sensory nerve sensitivity in the bladder and urethra in adult women with underactive bladder. We will then amplify sensory nerve activity via continuous electrical stimulation to improve LUTS associated with underactive bladder. Continuous direct electrical stimulation of the

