Study procedure visit: Participants will be reminded by phone call or email 48 hours before the study visit to withdraw from medications affecting urination per our inclusion criteria. On the day of the visit, participants will sign and date the informed consent document and complete a compensation form, LURN SI-29 questionnaire survey, and demographics questionnaire survey. Pre-procedure vital signs, point of care urinalysis, and a pregnancy test will be obtained. Participants will be excluded with a positive pregnancy test or delayed until resolution of infection with a positive urinalysis (per exclusion criteria). If participants have negative urinalysis, negative pregnancy test, and meet inclusion/exclusion criteria they will undergo current perception threshold (CPT) testing in the bladder and urethra.

Participants will be assigned to the intervention arm based on CPT. CPT data will be analyzed immediately by percentage change against normative data to stratify investigational allocation to intravesical (bladder) electrical stimulation or intraurethral electrical stimulation (Kenton et al. 2007). The allocation will be as follows: 1) if percentage change of urethral CPT > percentage change of bladder CPT then participants will receive intraurethral electrical stimulation, 2) if percentage change of bladder CPT > percentage change of

urethral CPT then participants will receive intravesical electrical stimulation, or 3) if percentage change of urethral CPT = percentage change of bladder CPT then participants will receive intravesical stimulation when cystometry "first desire to void" > 275ml or intraurethral stimulation when pressure-flow detrusor pressure at maximum flow < 30 cmH2O and maximum flow < 10 ml/s. After the investigational session of stimulation, participants will undergo post-study urodynamic studies which will include cystometry and pressure-flow studies. At the completion of these procedures, participants will be given standard urogynecology post urodynamic study instructions. They will also be instructed to complete remotely a post-study condition LURN SI-29 questionnaire that will be emailed via RedCap 7 days after the study visit. At that time, they will be considered to have completed the study.

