Uroflowmetry This standard procedure may be performed if participants are unable to void past the catheters in pressure flow studies. The dual chamber bladder catheter will be removed, and the participant will be instructed to void while sitting on a commode chair. A postvoid residual volume will be measured by straight catheterization. Variables that will be recorded include the following: voided volume, postvoid residual volume, flow rate, flow quality, and voided percentage. While this test sacrifices our secondary study objectives, we will still be able to fulfill our primary objectives of improved sensation and improved voiding function if the participant can void without catheters.

Selection of Subjects

• List inclusion/exclusion criteria and how subjects will be identified.

Inclusion Criteria:

- Females ages 18 and older
- Able to provide informed consent and agree to the study risks
- Willing to withdraw from medications affecting urination for the 48 hours prior to the procedure (e.g., alpha-adrenergic antagonists, cholinergic agonists, cholinesterase inhibitors)
- Has the below response to 2 of the 3 bulleted questions:
 - Questions regarding self-reported poor sensation during bladder filling or emptying (one or more of the below)

Question: In the past 7 days, where did you feel sensations when you felt you needed to urinate? Answer: "No" response for Bladder Area

Question: In the past 7 days, how often did you have no sensation of urine flow while you were urinating?

Answer: "Most of the time" or "Every time" response

Question: In the past 7 days, how often did you feel that your bladder was not completely empty after urination?

Answer: "Most of the time" or "Every time" response

Questions regarding self-reported bothersome urinary symptoms (one or more of the below)

Question: In the past 7 days, how satisfied were you with your bladder function? Answer: "Not at all satisfied" or "Somewhat satisfied" response

Question: In the past 7 days, how bothered were you by urinary symptoms?

Answer: "Very bothered" or "Extremely bothered" response

 Standard uroflowmetry with a voiding efficiency (voided volume / voided volume + residual volume) of < 80%, voided volume + residual volume must be >150ml for measurement

Exclusion Criteria:

- Preexisting neurological impairment (e.g., spinal cord injury, multiple sclerosis, Guillain-Barre, cauda equina syndrome, cerebrovascular accident, Parkinson's disease, traumatic brain injury)

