To account for participants failing to meet our eligibility criteria, it is anticipated that a total of 100 adult women will be screened to achieve n=20 total study participants. We expect to screen all patients with ICD codes suggestive of underactive bladder because a DEDUCE query revealed that in 2019 Duke Urogynecology clinics saw 34 patients meeting our criteria and approximately 10 of those patients went on for urodynamic studies. It is our expectation that the lack of consistent terminology and diagnostic parameters for underactive bladder will result in a large patient population failing to meet our eligibility criteria. Our expected enrollment will enable detection of a 7.5% change in voided percentage after stimulation with power (1-beta) of 0.8.

Statistical Methods

Primary Aim 1: Use of intraurethral electrical stimulation or intravesical electrical stimulation to assess increase in voided percentage during pressure-flow studies

Hypothesis: Electrical stimulation will increase voided percentage, and this hypothesis will be evaluated with non-parametric tests.

Method: Data will be analyzed by Wilcoxon signed-rank test to determine the influence of intravesical and intraurethral stimulation on bladder emptying.

Primary Aim 2: Use of LURN SI-29 questionnaire to assess whether electrical stimulation decreases urinary bothersome symptoms and increase bladder sensation during filling and emptying

Hypothesis: Intravesical (bladder) stimulation will decrease affirmatory responses to bothersome urinary symptoms and increase affirmatory responses to sensation during filling and emptying, whereas intraurethral stimulation will decrease affirmatory responses to bothersome symptoms during emptying.

Method: Data will be analyzed by the McNemar Exact Test or the Wilcoxon signed-rank test to determine the influence of intravesical or intraurethral stimulation on sensation.

Secondary Aim 1: Assess bladder or urethral current perception threshold (CPT) in women with underactive bladders

Hypothesis: Women with underactive bladder will have increased bladder CPT and increased urethral CPT (reduced sensory nerve activity) compared to normative data in asymptomatic women, and this hypothesis will be evaluated with the Dunn's multiple comparisons test.

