Method: Data will be analyzed by the Kruskall-Wallis test to determine the CPT distribution between women with underactive bladder and asymptomatic women.

Secondary Aim 2: Use of intravesical electrical stimulation to assess volumes at cystometric endpoints Hypothesis: Intravesical stimulation decrease cystometric volume endpoints, and this will be evaluated with the Bonferroni multiple comparisons correction. Method: Data will be analyzed by repeated measures ANOVA to determine the influence of intravesical on perceptions of bladder filling.

Secondary Aim 3: Use of intraurethral electrical stimulation to assess contraction strength and contraction duration

Hypothesis: Intraurethral stimulation will increase detrusor contraction strength and contraction duration, and this will be evaluated with non-parametric tests.

Method: Data will be analyzed by Wilcoxon signed-rank test to determine the influence of intraurethral stimulation on detrusor function.

Data & Safety Monitoring

Summarize safety concerns, and describe the methods to monitor research subjects and their data to
ensure their safety, including who will monitor the data, and the frequency of such monitoring. If a
data monitoring committee will be used, describe its operation, including stopping rules and frequency
of review, and if it is independent of the sponsor (per 45 CFR 46.111(a) (6)).

The paper informed consent and case report forms will be placed in individual participant binders, which will be stored under lock and key in the Duke Urogynecology office. Electronic informed consent will be stored in the REDCap project's File Repository. The regulatory binder will be an electronic regulatory binder in the Forte eRegulatory Management System (eReg). The research study staff will have access to these documents. The staff processing the participant reimbursement will have contact with the reimbursement form, which requires the participant provide a SSN. These forms will be kept in an opaque envelope and handled only by the research coordinator. Electronic data will be stored behind an enterprise-grade firewall in a shared folder on the password protected Duke PIN stations. It will not be placed on personal laptops, phones, or thumb drives.

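### Secondary Aim 1 compares CPT with external normative women without allowing for age, so if CPT rises with age and those women are younger, an age difference could be reported as reduced sensory nerve activity

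*Combined protocol and SAP*

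**What the plan says.** Under Statistical Methods, Secondary Aim 1, the hypothesis is that "Women with underactive bladder will have increased bladder CPT and increased urethral CPT (reduced sensory nerve activity) compared to normative data in asymptomatic women". The Method line reads "Data will be analyzed by the Kruskall-Wallis test to determine the CPT distribution between women with underactive bladder and asymptomatic women", and the Hypothesis line adds that "this hypothesis will be evaluated with the Dunn's multiple comparisons test". No age term, age matching, age strata or age-specific reference value is named there or elsewhere. The age distribution and size of the normative sample are not given.

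Three other places bear on age. Background & Significance describes underactive bladder symptoms as occurring "with the highest prevalence of symptoms in older men and women". Selection of Subjects admits "Females ages 18 and older", with no upper limit. At the study procedure visit participants complete the "LURN SI-29 questionnaire survey, and demographics questionnaire survey", but no planned analysis uses the demographic data.

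**The concern.** All 20 planned participants have underactive bladder, so the trial has no control group of its own for CPT. The contrast in Secondary Aim 1 is between a clinic sample and a reference sample recruited elsewhere. In such a contrast, any factor that both differs between the groups and affects CPT enters the difference, and a larger sample does not remove it. Age is the obvious candidate given the Background statement. The hypothesis leaves no room for it, because a higher CPT is equated directly with reduced sensory nerve activity.

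If CPT rises with age and the participants are the older group, the error runs in the hypothesised direction. A positive result could then reflect the ages of the two samples and not sensory dysfunction in underactive bladder.

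**Working it through.** **The plan's own figure.** No sample-size or power figure is given for Secondary Aim 1. The only one stated (n = 20, dz = 0.67, power 0.8) concerns voided percentage. A two-sided paired t-test at 5% with those inputs has power 0.811, so the figure reproduces; a one-sided test would give 0.893. The plan states no alpha, and this agreement is the reason for using two-sided 5% below.

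**Inputs.** From the documents: 20 participants, an external normative group, and a rank test without covariates. Assumed, because the documents do not give them: 40 normative women (20 and 50 also tried), an age gap of g standard deviations, and a CPT-age correlation r. True disease effect: none.

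**Model.** Age is normal with SD 1 and mean g in participants, 0 in normative women. CPT = r × age + √(1 − r²) × noise. CPT then has SD 1 in each group, and the groups differ by r × g SD through age alone.

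**Approximation.** For two groups, Kruskal-Wallis equals the two-sided Mann-Whitney test. With relative efficiency 0.955,

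δ = r × g × √(0.955 × n₁n₂/(n₁ + n₂)), and P(positive) ≈ Φ(δ − 1.96) + Φ(−δ − 1.96).

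For 20 and 40 women the root is √(0.955 × 800/60) = 3.568. At g = 1:

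- r = 0.2: δ = 0.714, about 11%
- r = 0.3: δ = 1.070, about 19%
- r = 0.5: δ = 1.784, about 43%

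**Simulation of the same model, unadjusted test.**

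| Normative n | Gap (SD) | r = 0.2 | r = 0.3 | r = 0.5 |
|---|---|---|---|---|
| 40 | 0.5 | 6% | 8% | 13% |
| 40 | 1.0 | 10% | 18% | 41% |
| 20 | 1.0 | 9% | 15% | 32% |
| 50 | 1.0 | 11% | 19% | 45% |

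With r = 0 or g = 0 the rate stays near 5%. At gaps of 1 SD or more, nearly all false positives are in the increased-CPT direction.

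**With age in the model.** Least-squares regression of CPT on group and age brings the rate back to about 4% to 6% in the settings checked.

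**Cost of adjusting.** Because age and group are correlated, the variance of the group coefficient is multiplied by 1 + p(1 − p)g², where p is the participants' share of the sample. With p = 20/60 and g = 1 this is 1 + (1/3)(2/3) = 1.222, so the standard error grows by √1.222 = 1.106. For a true effect of 0.8 SD with r = 0:

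- Unadjusted rank test: δ = 0.8 × 3.568 = 2.854, power about Φ(0.894) = 0.81; simulation gives about 0.80.
- Age-adjusted: δ = 0.8 × √(800/60)/1.106 = 0.8 × 3.651/1.106 = 2.64, power about Φ(0.68) = 0.75; simulation gives about 0.73.

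If only normative summaries exist, one can fit the age slope in the 20 participants and project their mean CPT to the normative mean age. In the same setting this has power of about 0.55. At r = 0.3 its standard error is about 0.352 against 0.272 unadjusted, 29% larger.

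**The case against.** The strongest reply is that the bias needs two facts that the documents do not supply: that CPT rises with age, and that the normative women are younger than the participants. If the samples are of similar age there is no bias from this source. If CPT rises with age and the normative women are older, the bias works against the hypothesis. This stands, and it makes the point conditional.

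A reader might infer from the Background that the plan expects its participants to be older than the normative women. It does not say so. The sentence describes symptom prevalence in the population, in both sexes, and makes no comparison with the reference sample. A reader might also infer that Secondary Aim 1 is biased as it stands; that does not follow either.

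The percentages are for one two-group test at 5%, whereas the plan also names Dunn's test. If Dunn's test corrected across six comparisons (two sites by three frequencies, an assumption), the rate at r = 0.3 and a 1 SD gap would be about 5% per comparison, not 18%. That is still well above the corrected level of 0.05/6 = 0.8%. Dunn's test deals with multiplicity and does not remove an age difference.

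Finally, this is a secondary aim of a study that calls itself a pilot, with no power claim attached. That limits the seriousness. It does not justify attributing an unadjusted difference to the disease.

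**Conclusion.** The point holds in conditional form. Secondary Aim 1 makes a non-randomised comparison with an external group, uses methods that cannot take age into account, and reads a higher CPT as reduced sensory nerve activity. If CPT rises with age and the normative women are younger, age alone could produce that result. With 20 against 40 women and a 1 SD gap, the false-positive rate of a single two-sided 5% test is about 10% to 41% for correlations of 0.2 to 0.5. With a 0.5 SD gap it is about 6% to 13%, and with no gap or no correlation about 5%. The normative sample size, the gap and the correlation are all assumed, so these figures illustrate the risk and do not estimate it.

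Because normative values also enter arm allocation ("CPT data will be analyzed immediately by percentage change against normative data to stratify investigational allocation"), a reader might infer that allocation is distorted by age too. The documents do not support this: the rule compares a woman's own bladder and urethral percentage changes, and an age effect proportionally equal at both sites would largely cancel. The primary aims and the n = 20 justification are unaffected. This is a cheap improvement to a secondary analysis.

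**What to change.** State the source, size and age distribution of the normative data in Secondary Aim 1.

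Where the normative values come with individual ages, make the main analysis a regression of log or ranked CPT on group and age, for each site and frequency, and keep Kruskal-Wallis as descriptive. Kruskal-Wallis already needs individual normative values, so the only further requirement is that ages accompany them.

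Where only summaries exist, report the normative age distribution beside the participants'. Give the participants' CPT estimated at the normative mean age as a sensitivity estimate with its interval, and no test. Do not attribute a difference to underactive bladder alone. The estimate rests on a linear slope from 20 women, may extrapolate, and must be on the scale that the normative source reports, so it should not be the deciding analysis.

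No new visit or procedure is needed for participants. The statistical cost is a wider interval when age and group are correlated: power of about 0.73 instead of 0.80 for a 0.8 SD effect at a 1 SD age gap with no CPT-age correlation. If ages do not already accompany the normative values, obtaining them is extra work.

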Official Title: AMPLIFY: Amplifying Sensation in Underactive Bladder

Protocol#: Pro00106457 Version 1.17

NCT#: NCT04516434

Document Date: 04/10/2024

Standard Research Summary

Purpose of the Study

Objectives & hypotheses to be tested

The overall objective of this study is to improve lower urinary tract symptoms (LUTS) in adult neurologically-intact women with underactive bladder through electrical stimulation of bladder sensory nerves or urethral sensory nerves. The first primary endpoints are that sensory nerve fiber stimulation to the bladder will decrease bothersome urinary symptoms during filling and emptying, stimulation to the urethra will decrease bothersome urinary symptoms during emptying, and that bladder stimulation will increase bladder sensation during filling and emptying, as determined by our lower urinary tract symptom questionnaire. The second primary endpoint is that sensory nerve fiber stimulation to the bladder or urethra will increase bladder emptying during pressure-flow studies in participants with poor baseline bladder function. In addition to these primary endpoints, we will also observe secondary endpoints that will be compared to paired baseline measurements. Secondary endpoints include (a) increased bladder or urethral current perception threshold relative to normative data, (b) decreased bladder volumes at cystometric endpoints with intravesical (bladder) electrical stimulation, and (c) increased detrusor contraction strength and contraction duration with intraurethral electrical stimulation.

Background & Significance

• Should support the scientific aims of the research

The storage and elimination of urine is regulated by neural circuits in the brain and spinal cord to coordinate function between the urinary bladder and the urethra (Fowler et al. 2008). During micturition (bladder emptying), the elimination of urine is facilitated by bladder muscle (detrusor) contraction and urethral and pelvic floor muscle relaxation. Urine flow through the urethra also activates sensory nerves to amplify bladder contractions and maintain efficient bladder emptying (Jung et al. 1999, Bump 2000). Incomplete emptying and urinary retention occur when these mechanisms are disrupted or poorly coordinated.

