"maximum cystometric capacity" with continuous intraurethral stimulation. Participants will be instructed to inform the study staff of any unpleasant sensations they may experience and may elect to terminate stimulation and participation at any point.

Cystometry After bladder stimulation or during intraurethral stimulation, standard urodynamics will be performed to assess bladder sensation and storage. Residual urine volume in the bladder will be removed by catheterization prior to cystometry. A dual-chamber 8-French catheter will be passed through the urethra into the bladder for retrograde filling. A second 8-French catheter will be placed in the vagina to measure intra-abdominal pressure. A stimulation electrode catheter will only be inserted in the intraurethral stimulation arm per the above methods. EMG pads will then be placed at 3 and 9 o'clock on each side of the perineum in an area not obstructed by hair or skin folds. These pads each have adhesive, which allows them to adhere in place through the study. Both the urethral and vaginal catheters will be zeroed to atmospheric pressure. The bladder will then be filled with room-temperature sterile saline solution in a retrograde fashion using a pump. Bladder sensation and urgency will be assessed while filling. Bladder pressure will be continuously observed and recorded during the study for evidence of involuntary detrusor contractions. The following values will be recorded from this portion of the study: volume of first sensation during bladder filling, first desire to void, strong desire to void, maximum cystometric capacity, presence or absence of detrusor overactivity.

Pressure-flow study A standard pressure flow study will be performed to evaluate voiding function after stimulation. The transurethral and intra-vaginal catheters are left in place after cystometry and the participant will be asked to void around them, into a commode. Bladder and abdominal pressures will be recorded, as well as urine flow over time. Variables that will be recorded in this portion of the study include the following: voided volume, postvoid residual volume, pressure at maximum flow, flow time, abdominal pressure during voiding, interrupted versus continuous flow, and pelvic floor muscle activity during micturition (as determined by EMG activity).

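### Secondary Aim 2 gives no rule for a cystometric sensation endpoint that is never reached, and complete-case repeated measures ANOVA would lose those women informatively

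*Combined protocol and SAP*

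**What the plan says.** Under Statistical Methods, Secondary Aim 2 concerns intravesical stimulation only and predicts lower volumes at the cystometric endpoints. The method is one sentence: "Data will be analyzed by repeated measures ANOVA to determine the influence of intravesical on perceptions of bladder filling". On multiplicity it adds that "this will be evaluated with the Bonferroni multiple comparisons correction", without giving the number of comparisons.

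The Cystometry procedure lists the volumes: "volume of first sensation during bladder filling, first desire to void, strong desire to void, maximum cystometric capacity". Purpose of the Study makes the comparison a paired one: "we will also observe secondary endpoints that will be compared to paired baseline measurements". With four volumes at two fills, a woman can contribute up to eight values.

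Two other places bear on who is in this analysis.

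- **Entry.** The inclusion criteria use the rule "Has the below response to 2 of the 3 bulleted questions". One of the three is headed "Questions regarding self-reported poor sensation during bladder filling or emptying"; the others are bother and a voiding efficiency below 80%.
- **Allocation.** Under Study procedure visit, a woman goes to the bladder arm when her bladder CPT departs more from normative data than her urethral CPT. On a tie, she goes there when first desire to void exceeds 275 ml.

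The documents contain no missing-data rule, censoring rule or analysis set for this aim.

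**The concern.** First sensation, first desire and strong desire are defined by the woman's report. If she reaches capacity without reporting one, that volume is not lost by accident. All that is known is that it lies beyond the volume infused, so the value is right-censored.

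Classical repeated measures ANOVA across endpoints and fills has no place for such a value. One empty cell out of eight removes the woman. The removal is informative: a woman with no first desire at baseline who reports one after stimulation has moved in the predicted direction, and she is excluded because of her baseline state. The remaining women understate the benefit, and a small arm becomes smaller. The bladder arm is also where this is most plausible, because allocation enriches it for reduced bladder sensitivity.

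**Working it through.** **The plan's own figure.** Data Analysis & Statistical Considerations gives n = 20, dz = 0.67 and power 0.80, tied to voided percentage. Alpha and sidedness are not stated; 0.05 two-sided is assumed. For a paired t-test the noncentrality is dz × √n = 0.67 × √20 = 3.00 on 19 df, which gives power 0.811, and 20 is the smallest n that reaches 0.80. The figure reproduces, but for all 20 women and a different outcome.

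**The bladder arm before any loss.** The plan fixes no split; 10 women is an assumption. Noncentrality is 0.67 × √10 = 2.12 on 9 df, so power is 0.47. At 0.05/4 = 0.0125 (Bonferroni over four volumes, also assumed) it is 0.23.

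**Loss of women at random.** Let q be the share of women with at least one empty cell. The number retained is Binomial(10, 1 − q), and power is averaged over it (alpha 0.05):

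| q | expected complete cases | power |
|---|---|---|
| 0% | 10 | 0.47 |
| 10% | 9 | 0.42 |
| 20% | 8 | 0.37 |
| 30% | 7 | 0.32 |
| 40% | 6 | 0.27 |

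At q = 20% the chance of losing at least one woman is 1 − 0.8^10 = 0.89. With other arm sizes, power at q = 20% is 0.16 (5 women), 0.56 (15) and 0.70 (20).

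**Loss that depends on the volume.** This is a simulation of one endpoint in 10 women (4,000 runs). All inputs except dz are assumed: baseline mean 300 ml, SD 100 ml, within-woman correlation 0.6, and one fixed capacity for all women and both fills. The true reduction is 0.67 × 100 × √(2 × (1 − 0.6)) = 59.9 ml. A volume above capacity is unreached. Capacity is set at 300 + 100 × z(1 − share unreached at baseline), which is 384 ml for 20%.

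| unreached at baseline | women retained | complete-case reduction | power, uncensored | power, complete-case | power, rank test keeping all |
|---|---|---|---|---|---|
| 10% | 8.9 | 54 ml | 0.47 | 0.38 | 0.44 |
| 20% | 7.8 | 51 ml | 0.46 | 0.31 | 0.41 |
| 30% | 6.6 | 47 ml | 0.47 | 0.24 | 0.38 |
| 40% | 5.6 | 44 ml | 0.47 | 0.19 | 0.35 |

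Repeat runs of the 20% case put the complete-case estimate at 51 to 53 ml, its power at 0.31 to 0.33 and the uncensored power at 0.46 to 0.48. The rank test here places an unreached value at the common capacity; with capacity fixed, this is close to ranking it above every observed volume. A paired t-test on complete pairs stands in for the ANOVA contrast. With several endpoints in one model, deletion for any empty cell removes at least as many women.

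**Substituting capacity.** Capacity is itself one of the volumes expected to fall. Take 10 women with no true change in the sensation volume, 20% unreached at baseline, and a capacity that falls by 60 ml after stimulation (all assumed). Entering capacity as the volume then creates a false reduction of 17 ml and rejects in the favourable direction about 12% of the time, against a nominal 2.5%.

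**The case against.** The strongest reply is that the plan does not say it will delete anyone. It names repeated measures ANOVA and stops there. The Bonferroni sentence fits separate baseline-to-post contrasts, in which a woman would be lost only for the endpoint she missed. Recording the capacity volume, or fitting a mixed model, is not ruled out. This stands: deletion is a property of the classical method, not a written rule. It does not remove the gap, because a contrast on complete pairs still loses the woman who gains that sensation.

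A reader might also infer that the trial selects women for absent bladder sensation. The documents do not support that. Poor sensation is one of three criteria with two needed, so bother plus low voiding efficiency suffices. Two of its three items concern emptying, and the third asks where the urge is felt, which presupposes an urge. A raised CPT or a late first desire points to a delayed endpoint, not necessarily a missing one. No frequency of unreached endpoints is given.

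Finally, the arm is weak mainly because it is small: power is 0.47 at 10 women with complete data. This is a secondary aim of a pilot study, and neither the primary aims nor the stated sample size is affected. All of this is fair and limits the weight of the point.

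**Conclusion.** The point holds as a gap in the specification with a predictable direction of error. The plan names a method that needs every cell, applies it to volumes that may not exist, and gives no rule for that case. If the method is run on complete cases, the women lost include those who show the predicted effect most clearly, and the estimate moves towards no effect.

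The size cannot be taken from the documents. On the assumed inputs, about 20% unreached at baseline takes the estimated reduction from 60 ml to about 51 to 53 ml and power from about 0.47 to about 0.32. A rank test that keeps these women recovers power to about 0.41. These figures depend on the assumed 10 women, the dz borrowed from voided percentage, the unreached rate and a stable capacity. If every woman reaches every endpoint, there is no loss. The documents do not support saying that the plan drops such women by rule, nor that entering capacity is a conservative remedy.

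**What to change.** Change the Secondary Aim 2 method as follows.

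1. Replace repeated measures ANOVA with a linear mixed model (stimulation, endpoint, their interaction, random intercept per woman) that keeps all bladder-arm women with their observed volumes.
2. Add a paired signed-rank test per endpoint in which an unreached endpoint ranks above every observed volume and unreached at both fills counts as no change.
3. Keep Bonferroni across the endpoints and state their number.
4. Report how many women reached each endpoint before and after stimulation.
5. Do not enter capacity as an exact volume in the main model; use it only as a labelled sensitivity analysis.

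Items 1 and 2 belong together. The mixed model keeps the women but does not by itself remove the bias: a woman with only a post-stimulation volume adds a value with no matching baseline, and the missing baseline is missing because it was high. The rank test and the counts are what credit her with a gain.

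The cost is protocol wording and slightly more analysis; no new measurement is needed beyond recording that an endpoint was not reached. The rank test loses power if capacity falls after stimulation and makes endpoints unreached at that fill.
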